12.6.2 Seizure Disorder

In patients with a history of seizure disorders, the worsening of seizures or change in seizure type will be reported as AEs and the type, duration, and frequency of occurrence will be recorded in the CRF. Patients who experience worsening of their seizure disorder should be withdrawn from the study.

A summary table of seizure activity will be sorted by SOC and PT. All seizures will be presented in a data listing.

12.6.3 Clinical Laboratory Evaluations

Laboratory parameters to be collected are listed in Appendix 6 will be summarized for the Double-Blind safety population and the Open-Label safety population. Laboratory data (hematology, serum chemistry, and urinalysis) will be converted to International System of Units (SI) for reporting and processing purposes. Absolute values and changes from Baseline will be presented descriptively.

Hematology, serum chemistry, and urinalysis will be summarized using descriptive statistics for numeric variables and numbers and percentages for categorical variables at each scheduled assessment. Numeric hematology, chemistry, and urinalysis results will be summarized using change from Baseline as well. Where it is applicable to categorize a laboratory assessment by Normal, High, or Low according to the normal range provided by the central laboratory, the lowest and highest post-baseline results will be compared with that at the study Baseline and the "shifts" from study Baseline will be summarized using the number and percentage of patients in each shift category by treatment group. The shift tables (for hematology and biochemistry) will also be provided for each of age groups (6 to <12 years; 12 to <18 years and 18 years or older) for the Double-Blind Treatment Phase. The same summaries by age groups may be repeated for the OLE Phase.

All clinical laboratory test results will be presented in the data listings. Laboratory values that are outside of the normal reference range will be flagged in the data listings.

Pregnancy tests and urine drug screen will be listed only.

12.6.4 Vital Signs

Vital signs will include blood pressure, heart rate, respiratory rate, weight, body temperature and height. Patients will be resting for at least minutes before taking vital signs.

Vital sign results and corresponding change from study Baseline values will be summarized at each scheduled visit using descriptive statistics by treatment group for Double-Blind safety population and Open-Label safety population.

All vital sign, body weight, and height measurements will be presented in a data listing.

Table 13 includes the normal ranges for the parameter of interest. Frequency count and percentage of patients with low/high vital signs will be tabulated at each visit and by treatment group. Shift from Baseline will also be provided. Results outside of the normal ranges will be flagged in the data listing. As the ranges are dependent on age, in the OLE, age will be derived at each visit. Those summaries by normal ranges will also be provided for each of age groups (6 to <12 years; 12 to <18 years and 18 years or older) for the Double-Blind Treatment Phase. The same summaries by age groups may be repeated for the OLE Phase.

Table 13: Vital Signs Normal Ranges by Age Group

Parameter	Low	High	Normal		
Children (6-12 years)	Children (6-12 years)				
Systolic Blood Pressure (mmHg)	< 80	> 120	80 – 120		
Diastolic Blood Pressure (mmHg)	< 55	> 70	55 – 70		
Heart Rate (beat per minutes)	< 70	> 110	70 – 110		
Respiration Rate (breath per minutes)	< 20	> 30	20 – 30		
Temperature (°C)	<35.5	>37.5	35.5 – 37.5		

Parameter	Low	High	Normal			
Weight (kg)	< 20	> 42	20 – 42			
Adolescent (13-17 years)	Adolescent (13-17 years)					
Systolic Blood Pressure (mmHg)	< 110	> 120	110 – 120			
Diastolic Blood Pressure (mmHg)	< 57	>71	57 – 71			
Heart Rate (beat per minutes)	< 55	> 105	55 – 105			
Respiration Rate (breath per minutes)	< 12	> 20	12 – 20			
Temperature (°C)	<36.3	>37.3	36.3 – 37.3			
Weight (kg)	< 50		≥ 50			
Adults (≥ 18 years)						
Systolic Blood Pressure (mmHg)	< 80	> 130	80 – 130			
Diastolic Blood Pressure (mmHg)	< 60	> 90	60 – 90			
Heart Rate (beat per minutes)	< 60	> 100	60 – 100			
Respiration Rate (breath per minutes)	< 12	> 20	12 -20			
Temperature (°C)	< 36.6	> 37.3	36.6 – 37.3			

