3. INVESTIGATIONAL PLAN AND ENDPOINTS

3.1. Description of the Study Design

3.1.1. Overall Study Design

This is a randomized, double-blind, placebo-controlled, parallel group, Phase 2 POC study in patients (ages 6 to 65 years) with PWS, followed by an optional OLE Phase.

The study will consist of a Screening Period (up to a maximum of 45 days), an 11-week Double-Blind Treatment Phase (including a Titration Period and an 8-week Stable Dose Period), and an optional OLE Phase. The OLE Phase will be multi-year in duration and will continue until the Sponsor elects to terminate the study. An overall schema of the study design is provided in Figure 1.

[figure not shown]
During Screening, patients who meet all eligibility criteria will be enrolled in the study, randomized in a 1:1:1 ratio to receive treatment with lower dose pitolisant, higher dose pitolisant, or matching placebo (20 patients per treatment group, ages 6 to 65 years) (Section 3.1.2). The lower and higher pitolisant doses, respectively in each age group, will be 8.9 mg and 17.8 mg for children ages 6 to <12 years, 13.35 mg and 26.7 mg for adolescents ages 12 to <18 years, and 17.8 mg and 35.6 mg for adults ages 18 to 65 years. In the Double-Blind Treatment Phase, patients will be titrated to their randomized stable dose of study drug during the Titration Period (Section 3.1.3). After completion of the Titration Period, patients will continue to take study drug at their randomized stable dose once daily in the morning upon wakening for an additional 8 weeks of blinded treatment (Stable Dose Period). The duration of the Double-Blind Treatment Phase will be 11 weeks.

Eligible patients who complete the Double-Blind Treatment Phase will be given the opportunity to participate in an optional OLE Phase.

In the OLE Phase, prior to implementation of Amendment 6, patients received a maximum target dose of pitolisant based on their age (17.8 mg for ages 6 to <12 years, 26.7 mg for ages 12 to <18 years, or 35.6 mg for ages 18 to 65 years; Section 3.1.4).

Safety, efficacy, and PK will be evaluated as detailed in Section 3.1.3 (Double-Blind Treatment Phase) and Section 3.1.4 (OLE Phase).

Figure 1: Overall Study Design

AE = adverse event; EOT = End of Treatment; F-Up = follow-up; OLE = Open Label Extension; PK = pharmacokinetics; TC = telephone call; V = Visit.

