4.1.1. Inclusion Criteria

Each patient must meet all of the following criteria to be enrolled in this study:

- 1. Is able to provide voluntary, written informed consent (patient or parent[s]/legal guardian[s]) and, where applicable, voluntary, written assent (patient, as appropriate).
- 2. Has a diagnosis of PWS confirmed by genetic testing and patient medical records. Genetic testing will be provided by the Sponsor, if not confirmed based on the review of the patient's medical records.
- 3. Male or female patients ages 6 to 65 years at the time of enrollment.
- 4. Demonstrates adequate sleep duration via patient sleep diary during Screening defined as at least 8 hours of sleep per night for patients ages 6 to <12 years, at least 7 hours for patients ages 12 to <18 years, or at least 6 hours for patients ages ≥18 years, based on the mean number of hours from up to 14 nights (at least 7 nights must be recorded for evaluation).
- 5. Has EDS as determined by ESS-CHAD (parent/caregiver version) score \geq 12.
- 6. If taking hormone treatments (including growth hormone, testosterone, and estrogen supplements) and/or allowed chronic concomitant medication or supplements, patient must be on a stable dose of these medications for 3 months prior to randomization and for the duration of the Double-Blind Treatment Phase of the study; 10% variability in hormone dose is allowed.
- 7. If taking a wake-promoting treatment that could affect EDS (including stimulants, modafinil, and armodafinil), must be on a stable dose for at least 28 days prior to Screening and remain on a stable dose during the Double-Blind Treatment Phase of the study (dose adjustments will be permitted in the OLE Phase) or agree to wash out of treatment for 5 half-lives or 14 days, whichever is longer.
- 8. If taking a chronically administered sedating medication for management of behavioral manifestations (e.g., hypnotics, benzodiazepines, antipsychotics, alpha agonists, anticholinergics, and antidepressants) must be on a stable dose for at least 28 days prior to Screening and remain on a stable dose during the Double-Blind Treatment Phase of the study (dose adjustments will be permitted in the OLE Phase) or agree to wash out of treatment for 5 half-lives or 14 days, whichever is longer.

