6.5.2. Physical Examinations

Full or abbreviated physical examinations will be performed at study visits as detailed in Section 7. Full physical examinations will include an evaluation of the head and neck as well as cardiovascular, respiratory, gastrointestinal, neurological, dermatological, and musculoskeletal systems. Abbreviated physical examinations will be performed based on patient/caregiver-reported symptoms.

Height and weight will be measured using standardized methods and recorded on a standardized growth chart per Centers for Disease Control and Prevention (CDC) recommendations (CDC Clinical Growth Charts). Height will be recorded at Screening and at the EOT/ET Visit during the Double-Blind Treatment Phase and at every on-site visit during the OLE Phase. Body weight will be recorded at every on-site study visit.

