9.3 Baseline

For the Double-Blind Treatment Phase, Baseline is defined as the last record or measure collected prior to the study drug administration. For the OLE Phase, Baseline will be identical to the Double-Blind Treatment Phase, i.e., the last non-missing record or measure collected prior to study drug administration.

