12.6 Safety Analyses

All safety analyses will be completed for the Double-Blind safety and Open-Label safety populations. All safety data will be listed and summarized. No formal statistics will be performed for the safety analysis.

For the Double-Blind Treatment Phase, summaries will be presented by treatment arms and active arms pooled; for the OLE Phase, results will be tabulated for the overall group.

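### In the uncontrolled, multi-year OLE, weight and height are summarised as raw change pooled over ages 6 to 65, so the mean-change table cannot separate a drug effect from normal growth in minors

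*SAP*

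**What the plan says.** SAP 12.6.4 defines the variables: "Vital signs will include blood pressure, heart rate, respiratory rate, weight, body temperature and height". For all of them, "Vital sign results and corresponding change from study Baseline values will be summarized at each scheduled visit using descriptive statistics by treatment group", in both the double-blind and the open-label safety populations.

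Four other provisions decide what this means in the OLE:

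- **Baseline** (SAP 9.3): "For the OLE Phase, Baseline will be identical to the Double-Blind Treatment Phase". Change therefore accumulates from before the first double-blind dose.
- **Grouping** (SAP 12.6): "for the OLE Phase, results will be tabulated for the overall group".
- **Age range** (Protocol 4.1.1): "Male or female patients ages 6 to 65 years at the time of enrollment".
- **Duration** (Protocol 3.1.1): "The OLE Phase will be multi-year in duration and will continue until the Sponsor elects to terminate the study".

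SAP 12.6.4 also has a categorical analysis. Table 13 sets low and high limits by age band, and counts and shifts from Baseline are tabulated. "As the ranges are dependent on age, in the OLE, age will be derived at each visit". Versions by age group are planned for the double-blind phase and are optional for the OLE.

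Protocol 6.5.2 requires height and weight to be "recorded on a standardized growth chart per Centers for Disease Control and Prevention (CDC) recommendations". The SAP repeats the growth-chart note in its assessment schedules, but no SAP analysis uses it. The SAP plans no z-score, percentile or growth velocity, and BMI is summarised at Baseline only (SAP 12.2.1).

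**The concern.** A raw change in kilograms or centimetres means something different in a 7-year-old and in a 40-year-old. Over weeks this hardly matters. Over years, a child who tracks a growth percentile exactly shows a steadily rising change from Baseline. With no control arm and all ages in one row, the reader of the OLE table cannot tell how much of the mean is growth.

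Weight and growth are not incidental here. Protocol 1.1 lists short stature, hyperphagia and early childhood obesity among the features of PWS, hyperphagia is an exploratory objective (Protocol 2.3), and long-term safety is a secondary objective in the protocol synopsis and SAP 7.2. The raw table could make an inert drug look as if it causes weight gain. It could equally let a slowing of growth, or a loss of weight relative to age, pass as ordinary gain.

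**Working it through.** The plan gives no figure for expected weight or height change, so there is none to reproduce. The check has two parts: the size of the growth component, and whether Table 13 removes it.

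**1. Growth component of the pooled mean**

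Inputs from the documents: Visit 9 is at Day 369. On-site visits follow at Day 549 and every 180 days after that, so one falls at 549 + 3 × 180 = Day 1089.

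Inputs not in the documents, assumed as ranges: minors gain 2 to 5 kg and 4 to 7 cm per year; minors make up 1/3 to 2/3 of patients; adults do not change; there is no drug effect.

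Formula: pooled mean change = share of minors × yearly gain × (day / 365.25).

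| | Day 369 (1.01 years) | Day 1089 (2.98 years) |
|---|---|---|
| One child, kg | 2 × 1.01 = 2.0 to 5 × 1.01 = 5.1 | 6.0 to 14.9 |
| One child, cm | 4.0 to 7.1 | 11.9 to 20.9 |
| Pooled, kg | 1/3 × 2 × 1.01 = 0.7 to 2/3 × 5 × 1.01 = 3.4 | 2.0 to 9.9 |

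On an age- and sex-standardised scale, the same child tracking one percentile has an expected change of 0 at every visit.

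The raw mean cannot be decomposed. A gain of +3 kg per year in minors arises equally from growth of 3 with a drug effect of 0, and from growth of 5 with a drug effect of −2.

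**2. Whether Table 13 corrects for growth**

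Weight limits: ages 6–12, low below 20 kg and high above 42 kg; ages 13–17, low below 50 kg with no upper limit; adults, none. Height has no limits at any age.

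- Within ages 6–12, a child can go from 21 to 41 kg and stay normal throughout.
- At the 13th birthday an unchanged weight changes category: 20 to 42 kg goes from normal to low, above 42 and below 50 kg from high to low, and 50 kg or more from high to normal. A child at a constant 45 kg is high at 12 and low at 13. Because age is re-derived at each OLE visit, these moves enter the shift table.
- A patient who turns 18 in the OLE no longer has a weight category.
- For height, the raw summary is the only one planned.

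**3. The double-blind phase, for contrast**

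Day 77 is 77 / 365.25 = 0.21 years. The same assumed rates give 0.4 to 1.1 kg and 0.8 to 1.5 cm per child, expected equally in the placebo arm. The raw comparison between arms is interpretable there.

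**The case against.** The strongest reply is that the SAP does not rely on raw change alone and that the trial has other ways to notice a problem. Weight is classified by age band at each visit, with shifts. The 11-week phase has a concurrent placebo group. Height and weight are charted against CDC references during conduct, clinically significant findings are recorded as adverse events (Protocol 6.5.1), and every weight and height is listed. Neither growth nor weight is a named safety endpoint (Protocol 3.2.3), Protocol 1.4 reports no clinically relevant effect on vital signs, and safety analysis is descriptive in a proof-of-concept study.

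Most of this stands, and it limits the point. A reader might infer that a weight or growth effect could not be seen anywhere in the trial. The documents do not support that: the placebo comparison, the growth charts, the adverse event reports and the listings all remain. A reader might also infer that weight is analysed only as raw change. Table 13 shows otherwise, although it does not correct for growth.

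A reader might read Table 13's child band as a trajectory, (42 − 20) kg over six or seven years, and take a yearly gain from it. It is one normal range for every child aged 6 to 12 and mixes position in the range with growth, so no rate follows from it.

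It is also fair that z-scores do not deliver attribution. Growth hormone must be stable only through the double-blind phase (Protocol 4.1.1, criterion 6), and PWS has its own growth and weight course. Without a control, a drift in z-score may reflect either.

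**Conclusion.** The point holds for the OLE summaries. Their mean change in weight and height combines normal growth in minors with any drug effect, and nothing else in the planned tables separates the two. That follows from the text and does not depend on the assumed rates.

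The size does depend on them. Under the assumptions stated, growth alone contributes about +0.7 to +3.4 kg to the pooled mean at Day 369, and more later. Neither the growth rate nor the age mix is in the documents, and randomisation is not stratified by age (Protocol 3.1.2), so a single figure would not be justified.

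No efficacy conclusion is affected, and the double-blind comparison remains usable. This is an inexpensive improvement to a long-term safety display.

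**What to change.** In SAP 12.6.4:

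1. For patients under 18 in the OLE, derive weight-, height- and BMI-for-age z-scores against the CDC reference, using sex and age at visit. Summarise each value and its change from Baseline at every OLE visit where the measurements exist.
2. Make the OLE weight and height summaries by age group mandatory, with adults shown separately, and state how a patient who turns 18 during the OLE is handled.
3. In the double-blind phase, derive weight z-scores at each visit, by arm. Derive height and BMI z-scores only at Screening/Baseline and at the end-of-treatment or early-termination visit, because height is not scheduled at Visits 3 and 4 (Protocol 6.5.2).
4. Keep the existing raw summaries for all patients.
5. State the limits beside the table: values may be extreme in PWS against a general-population reference, and OLE drift may reflect disease course or growth hormone changes.

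The cost is a paragraph of SAP text and one derivation. Date of birth, sex, weight and height are already collected, and age at each OLE visit is already to be derived. The SAP is written against Amendment 5 and allows for updates after protocol changes (SAP 6.0), and the OLE has its own later study report (SAP 9.6), so there is a natural place to add this.

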8.0 Study Design

8.1 General Design

This is a randomized, double-blind, placebo-controlled, parallel group, Phase 2 proof of concept study in patients (ages 6 to 65 years) with PWS, followed by an optional OLE Phase.

The study will consist of a Screening Period (up to a maximum of 45 days), an 11-week Double-Blind Treatment Phase (including a 3-week Titration Period and an 8-week Stable Dose

Period), and an optional OLE Phase. The OLE Phase is expected to be multi-year in duration. An overall schema of the study design is provided in Figure 1.

During Screening, patients who meet all eligibility criteria will be randomized in a 1:1:1 ratio to receive treatment with low dose pitolisant, high dose pitolisant, or matching placebo (approximately patients per treatment group, ages 6 to 65 years). The low and high pitolisant doses, respectively in each age group, will be 8.9 mg and 17.8 mg for children ages 6 to <12 years, 13.35 mg and 26.7 mg for adolescents ages 12 to <18 years, and 17.8 mg and 35.6 mg for adults ages 18 to 65 years.

[figure not shown]
The day after the Baseline Visit, patients will take their first dose of study drug. In the Double-Blind Treatment Phase, patients will be titrated to their randomized stable dose of study drug during the 3-week Titration Period; study drug dose will be titrated on Day 8 and again on Day 15 (based on randomized stable dose, per Table 1, with all patients at their randomized stable dose by Day 15). After completion of the 3-week Titration Period, patients will continue to take study drug at their randomized stable dose for an additional 8 weeks of blinded treatment (Stable Dose Period; Days 22 to 77). The duration of the Double-Blind Treatment Phase will be 11 weeks.

Adjustments to study drug dosing outside the protocol-specified titration schedule are not permitted during the 11-week Double-Blind Treatment Phase of the study.

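### SAP Table 13 vital-sign limits use age bands that differ from the reporting age groups, carry an unexplained 110-120 mmHg adolescent systolic range, and in the OLE can produce category shifts with no change in value

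*SAP*

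**What the plan says.** SAP section 12.6.4 sets the limits in Table 13. The first two bands are labelled "Children (6-12 years") and "Adolescent (13-17 years"); the third is adults of 18 or older.

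Three outputs use these limits:

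- Counts: "Frequency count and percentage of patients with low/high vital signs will be tabulated at each visit and by treatment group".
- Shifts: "Shift from Baseline will also be provided".
- Flags on out-of-range results in the listings.

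The counts and shifts are repeated for "each of age groups (6 to <12 years; 12 to <18 years and 18 years or older") in the Double-Blind Treatment Phase, and may be repeated by age group for the OLE. These are also the dosing groups: SAP section 8.1 gives "13.35 mg and 26.7 mg for adolescents ages 12 to <18 years".

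On which age picks the band, the SAP says only: "As the ranges are dependent on age, in the OLE, age will be derived at each visit". SAP section 9.3 keeps the pre-double-blind Baseline for the OLE, and section 8.1 expects the OLE to last several years.

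**The concern.** A patient of 12 belongs to the adolescent group for dosing and reporting but to the child band for limits. The adolescent low/high table therefore mixes two sets of limits, and they differ for every parameter.

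The adolescent systolic range is also out of line within its own table. The lower limit rises by 30 mmHg at 13 and falls by 30 mmHg at 18. Nothing in the documents explains this.

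In the OLE, Baseline is most naturally judged on age at Baseline and each later value on age at that visit. A shift can then record a birthday rather than a change in the patient. The OLE is tabulated as one overall group (SAP sections 10.0 and 12.6), so there is no concurrent arm against which to recognise such shifts.

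At stake is how readable these tables are. Safety is part of the primary objective and vital signs are a named safety endpoint. Safety analysis is descriptive only, so the tables will be read as they stand.

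**Working it through.** The plan states no expected flag rate, so there is no figure to reproduce.

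**1. Bands against reporting groups**

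| Age | Table 13 limits | Reporting group |
|---|---|---|
| 6 to <12 | Child | 6 to <12 |
| 12 | Child | 12 to <18 |
| 13 to 17 | Adolescent | 12 to <18 |
| 18 or older | Adult | 18 or older |

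The mismatch concerns 12-year-olds only; the cut at 18 agrees. Reading the child label as ending at the 12th birthday would not help, because 12-year-olds would then have no limits at all. By contrast, the QTcF summary groups in SAP section 12.6.6 (6 to <10, 10 to <20, 20 to 65) match their thresholds.

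**2. Systolic limits (mmHg, Table 13)**

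- Child: 80-120, width 40.
- Adolescent: 110-120, width 10.
- Adult: 80-130, width 50.
- Step in the lower limit at 13 and at 18: 110 − 80 = 30.

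**3. Unchanged values that change category**

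Each whole-number value (steps of 0.1 for temperature) was classified under adjacent bands as low (L), normal (N) or high (H).

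| Parameter | At 13 | At 18 |
|---|---|---|
| Systolic BP | 80-109 N→L | 80-109 L→N; 121-130 H→N |
| Diastolic BP | 55-56 N→L; 71 H→N | 57-59 N→L; 72-90 H→N |
| Heart rate | 55-69 L→N; 106-110 N→H | 55-59 N→L; 101-105 N→H |
| Respiratory rate | 12-19 L→N; 21-30 N→H | none |
| Temperature (°C) | 35.5-36.2 N→L; 37.4-37.5 N→H | 36.3-36.5 N→L |
| Weight (kg) | 20-42 N→L; 43-49 H→L; 50 or more H→N | not compared (no adult limits visible) |

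So a systolic pressure of 105 is normal at 12, low at 13-17 and normal at 18. A weight of 45 kg goes from high (above 42) to low (below 50) at 13.

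**4. Share of adolescent systolic readings outside 110-120**

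The mean m and SD are assumptions; the documents give neither. With a normal distribution,

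share = 1 − [Φ((120 − m)/SD) − Φ((110 − m)/SD)].

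For m = 115 and SD = 10: 1 − [Φ(0.5) − Φ(−0.5)] = 0.617.

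| Mean | SD 5 | SD 7 | SD 8 | SD 10 | SD 12 | SD 15 |
|---|---|---|---|---|---|---|
| 115 | 32% | 48% | 53% | 62% | 68% | 74% |
| 110 or 120 | 52% | 58% | 61% | 66% | 70% | 75% |
| 105 or 125 | 84% | 78% | 76% | 76% | 77% | 79% |

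With the mean at mid-range, the share passes one half at SD = 5/z(0.75) = 5/0.6745 = 7.4 mmHg. If readings are rounded to whole mmHg it does so at 5.5/0.6745 = 8.2 mmHg. With that rounding, a mean of 110 or 120 and SD 5 gives 48%.

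**The case against.** Four stronger readings are tempting, and the documents do not support them.

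- **Most adolescents will be flagged.** A reader might take this as fact from a 10 mmHg range. No mean or SD is given, and with a mean of 115 and an SD of 7 or less the share is below half. The age mismatch does not drive the flag rate either; the narrow range does.
- **The flags are mostly false.** That presumes the limits are wrong. The source of Table 13 is not in the documents, and the contrast between bands justifies a query, not a conclusion.
- **A real blood pressure effect would be buried.** SAP section 12.6.4 also summarises actual values and change from Baseline by visit and treatment group, independently of Table 13. Clinically significant vital signs are recorded as adverse events (Protocol section 6.5.1), and these are summarised by age group (SAP section 12.6.1). In the double-blind phase the same limits apply to every arm, so heavy flagging blunts the categorical table but does not in itself favour an arm.
- **Category changes at birthdays affect the whole trial.** The rule of deriving age at each visit is stated for the OLE only. It reaches only patients who pass 13 or 18 with a value in the intervals above, and it distorts no randomised comparison.

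It is also fair to say that deriving age at each visit is reasonable in growing patients. Freezing the band at Baseline age would flag a patient enrolled at 11 as high at 15 for 50 kg and low for a respiratory rate of 16, both normal on the adolescent limits. It would also carry the 110-120 range into adulthood for a patient enrolled at 17.

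All of this limits the point's reach. It leaves standing the mismatch at age 12, the systolic discontinuity and the OLE shifts without a change in value.

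**Conclusion.** The point holds as a minor error in the written rules. Followed exactly, they judge 12-year-olds on child limits within the adolescent summary and let OLE shift tables record birthdays as changes in vital signs. Both follow from the SAP text without assumptions, beyond the natural reading that Baseline is judged on age at Baseline. The number of patients affected cannot be derived from the documents.

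The adolescent systolic range needs checking because it is inconsistent with both of its neighbours. Its effect on the flag rate rests on assumed values: probably more than half of readings if the SD is about 8 mmHg or more or the mean is away from 115, and as low as about a third at mean 115 and SD 5.

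The consequences stop at the descriptive categorical safety tables and listings. Efficacy is untouched, and the summaries of actual values and change from Baseline remain valid.

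**What to change.** 1. Align the Table 13 bands with 6 to <12, 12 to <18 and 18 or older.
2. First verify the adolescent systolic limits against their source, and correct or justify them, because alignment moves 12-year-olds into that band. No replacement limits are proposed here; these are reporting flags, not rules of care.
3. In OLE shift tables, count a shift only when the Baseline and post-baseline values are judged on the same limits. Show patients who change band separately.
4. Keep age-at-visit limits for the by-visit OLE flags, and do not freeze the band at Baseline age. State which age applies in the double-blind phase, where the SAP is silent.

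**Cost.** One table, one programming rule and a documented SAP update. Fewer patients contribute to the OLE shift table. Protocol section 1.3.2 describes the double-blind phase as completed, so any change to its tables would be post hoc and should be labelled as such. The OLE has its own later report (SAP section 9.6). The SAP was written to Amendment 5 and provides for updates after protocol changes (section 6.0); Amendment 6 followed, so there is a natural occasion to make the change.
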